3.2. Duration of Treatment

The treatment duration in this study is up to a maximum of 54 months inclusive of the 18-month Treatment Period, potential time on the Legacy Treatment Extension Period prior to transition to the RTE Period, and an 18-month RTE Period.

Refer to Section 4.3.1 for information on early treatment discontinuation.

3.3. Duration of Study

The estimated time on study for each patient is a maximum of 5 years, inclusive of 42 days of Screening and up to 54 months of open-label treatment (including 18 months in the Treatment Period, 0 to 18 months as applicable in the Legacy Treatment Extension Period, and 18 months in the Randomized Treatment Extension Period), plus the Follow-up Period of up to 1 year.

The Follow-up Period is until serum TTR levels return to $\geq 80\%$ of baseline (for up to 1 year after the last dose of study drug), or until the patient starts a TTR lowering regimen as a part of clinical care, whichever comes first; all patients will be followed for a minimum of 3 months. Female patients of child-bearing potential who discontinue ALN-TTRSC02 will be followed until serum TTR levels return to $\geq 80\%$ of baseline.

3.3.1. Definition of End of Study for an Individual Patient

A patient is considered to have reached the end of the study if:

- [REDACTED]
- the patient has completed the ALN-TTRSC02 Follow-up Period, until serum TTR levels return to $\geq 80\%$ of baseline (for a maximum of up to 1 year after the last dose of study drug), or until the patient starts a TTR lowering regimen as a part of clinical care, whichever comes first; all patients will be followed for a minimum of 3 months. Female patients of child-bearing potential who discontinue ALN-TTRSC02 will be followed until serum TTR levels return to $\geq 80\%$ of baseline.

3.4. Number of Planned Patients

[figure not shown]
Approximately 160 patients are planned for enrollment in this study.

To match the cardiac disease severity with the APOLLO study population, the study plans to enroll no more than 15% of patients with NT-proBNP values greater than 3000 ng/L at baseline.

3.5. Method of Assigning Patients to Treatment Groups

Using the Interactive Response System (IRS), patients will be randomized 3:1 to the ALN-TTRSC02 or patisiran arm. Randomization will be stratified by TTR genotype (V30M vs. non-V30M) and baseline NIS score (<50 vs \geq 50).

Each patient will be uniquely identified in the study by a combination of the site number and patient identification number. Upon signing the informed consent form (ICF), the patient will be assigned a patient identification number by the IRS. The Investigator or his/her designee will contact the IRS to randomize the patient after confirming that the patient fulfills all the inclusion criteria and none of the exclusion criteria.

3.6. Blinding

Not applicable, this is an open-label, controlled study.

3.7. Data Monitoring Committee

An independent Data Monitoring Committee (DMC) will oversee the safety and overall conduct of this study through the Treatment Period (through Month 18), providing input to the Sponsor. The DMC will operate under the rules of a charter that will be reviewed and approved at the organizational meeting of the DMC. The DMC has the responsibility for reviewing safety data and analyses and making recommendations to the Sponsor. The DMC will perform periodic reviews of data during the course of the clinical trial through the Treatment Period, and on an ad hoc basis for review of emergent safety data. Details are provided in the DMC Charter.

3.8. Adjudication Committee

An independent Adjudication Committee will review deaths and will attribute a cause according to the responsible underlying disease process rather than the immediate mechanism. Deaths will be classified as specified in the Adjudication Committee Charter.

4. SELECTION AND WITHDRAWAL OF PATIENTS

Each patient must meet all of the following eligibility criteria at Screening Visit 1 (except where specified) to be eligible for enrollment in the study.

4.1. Inclusion Criteria

Patients are eligible to be included in the study if all of the following criteria apply:

Age and Sex

1. Male or female age 18 (or age of legal consent, whichever is older) to 85 years of age

Patient and Disease Characteristics

2. Have a diagnosis of hATTR amyloidosis with documented TTR mutation
3. Have a NIS of 5 to 130 (inclusive; this criterion must be met at the Screening Visit 2)
4. Have a PND score of $\leq 3b$ (this criterion must be met at the Screening Visit 2)
5. Have a Karnofsky Performance Status (KPS) of $\geq 60\%$

Informed Consent

6. Patient is willing and able to comply with the study requirements and to provide written informed consent

4.2. Exclusion Criteria

Patients are excluded from the study if any of the following criteria apply:

Disease-specific Conditions

1. Has had a liver transplant or is likely, in the opinion of the Investigator, to undergo liver transplantation during the 18-month Treatment Period of the study
2. Has known other (non-hATTR) forms of amyloidosis or clinical evidence of leptomeningeal amyloidosis
3. Has a New York Heart Association heart failure classification >2

Laboratory Assessments

4. Has any of the following laboratory parameter assessments:
 - a. ALT and/or AST $>1.5\times$ upper limit of normal reference range (ULN)
 - b. Total bilirubin $>ULN$ (>1.5 ULN in patients with Gilbert's Syndrome)
 - c. International normalized ratio (INR) >1.2 (patients on anticoagulant therapy with an INR of ≤ 3.5 will be allowed)

(Note: ALT, AST, and total bilirubin laboratory criteria must be met at both Screening Visit 1 and Screening Visit 2)
5. Platelet count $<50,000/\mu\text{L}$
6. Absolute neutrophil count (ANC) <1500 cells/ mm^3
7. Estimated glomerular filtration rate (eGFR) ≤ 30 mL/min/ 1.73m^2 (using the Modification of Diet in Renal Disease [MDRD] formula)
8. Has vitamin B12 levels below the lower limit of normal (LLN)

9. Has known human immunodeficiency virus (HIV) infection; or evidence of acute or chronic hepatitis C virus (HCV) or hepatitis B virus (HBV) infection

Prior/Concomitant Therapy

10. Current or future participation in another investigational device or drug study, scheduled to occur during this study, or has received an investigational agent or device within 30 days (or 5 half-lives of the investigational drug, whichever is longer) prior to dosing (Day 1)
11. Received prior TTR-lowering treatment or participated in a gene therapy trial for hATTR amyloidosis
12. Is currently taking tafamidis, doxycycline, or tauroursodeoxycholic acid; if previously on any of these agents, must have completed a 14-day wash-out prior to dosing (Day 1)
13. Is currently taking diflunisal; if previously on this agent, must have at least a 3-day wash-out prior to dosing (Day 1)

Medical Conditions

14. Has other known causes of sensorimotor or autonomic neuropathy (eg, autoimmune disease, monoclonal gammopathy) that the treating physician believes to be contributing to the neuropathy
15. Had acute coronary syndrome within the past 3 months
16. Has uncontrolled clinically significant cardiac arrhythmia or unstable angina
17. Has known type 1 diabetes
18. Has had type 2 diabetes mellitus for ≥ 5 years
19. Has untreated hypo- or hyperthyroidism
20. Has had a major surgery within the past 3 months or has a major surgery planned during the study through Month 18
21. Has an active infection requiring systemic antiviral, antiparasitic or antimicrobial therapy that will not be completed prior dosing (Day 1)
22. Had a malignancy within 2 years, except for basal or squamous cell carcinoma of the skin or carcinoma in situ of the cervix that has been successfully treated
23. Anticipated survival is less than 2 years, in the opinion of the Investigator
24. History of multiple drug allergies; or history of allergic reaction to an oligonucleotide or GalNAc; or had a prior severe reaction to a liposomal product or any component of patisiran (ALN-TTR02)
25. Is unable to take the required premedications (see Section 5.2.2.2)
26. History of intolerance to subcutaneous (SC) injection(s) or significant abdominal scarring that could potentially hinder study drug administration or evaluation of local tolerability
27. Any condition (eg, medical concern), which in the opinion of the Investigator, would make the patient unsuitable for dosing or which could interfere with the study

compliance, the patient's safety and/or the patient's participation through the Month 18 visit of the study. This includes significant active and poorly controlled (unstable) cardiovascular, neurologic, gastrointestinal, endocrine, renal or psychiatric disorders unrelated to hATTR identified by key laboratory abnormalities or medical history

Contraception, Pregnancy, and Breastfeeding

28. Is not willing to comply with the contraceptive requirements during the study period, as described in Section 5.6.1.
29. Female patient is pregnant or breastfeeding

Alcohol Use

30. Unwilling or unable to limit alcohol consumption throughout the course of the study. Alcohol intake of >2 units/day is excluded during the study (unit: 1 glass of wine [approximately 125 mL] = 1 measure of spirits [approximately 1 fluid ounce] = ½ pint of beer [approximately 284 mL])
31. History of alcohol abuse, within the last 12 months before screening, in the opinion of the Investigator

4.3. Removal from Therapy or Assessment

Patients or their legal guardians are free to discontinue study drug and/or stop protocol procedural assessments, or participation in the study as a whole at any time and for any reason, without penalty to their continuing medical care. The Investigator or the Sponsor may discontinue study drug or stop a patient's participation in the study at any time if this is considered to be in the patient's best interest. Any discontinuation of treatment or the stopping of the patient's participation in the study must be fully documented and recorded in the electronic case report form (eCRF) and should be followed up by the Investigator.

Discontinuation of study drug or declining procedural assessments is described in Section 4.3.1, while the stopping of a patient's participation in the study is detailed in Section 4.3.2.

4.3.1. Discontinuation of Study Drug or Declining Procedural Assessments

Reasons for discontinuation of study drug include any of the following:

- Significant violation of the protocol
- Adverse Event
- Non-adherence to treatment regimen
- Pregnancy
- Lost to follow-up
- Other reason (non-adverse event)
- Or, the study is terminated by the Sponsor

If possible, the Investigator will confer with the Sponsor or Medical Monitor before discontinuing dosing of the patient. Patients who are pregnant will be discontinued from study

drug dosing immediately (see Section 6.5.7.7 for reporting and follow-up of pregnancy). A positive urine pregnancy test should be confirmed by a serum pregnancy test prior to discontinuing the study drug.

Patients who discontinue study drug and/or decline procedural assessments should not be automatically removed from study. In general, patients who discontinue study drug dosing for any reason will be encouraged to remain on the study to complete the remaining assessments so that their experience (including, at a minimum, information on vital status, cardiac transplant procedures, LVAD placement and hospitalizations for the duration of the study) is captured in the final analyses.

If this occurs, the Investigator is to discuss with the patient the appropriate processes for discontinuation from study drug and must discuss with the subject the options for continuation of the Schedule of Assessments (Table 3), including different options for follow-up and collection of data (eg, in person, by phone, by mail, through family or friends, or from options not involving patient contact, such as communication with other treating physicians, or from review of medical records), including endpoints and adverse events, and must document this decision in the patient's medical records.

If a patient discontinues dosing due to an AE, including serious adverse events (SAEs), the event should be followed as described in Section 6.5.7. When a patient discontinues study drug dosing, the primary reason must be recorded in the electronic case report form (eCRF). Patients who discontinue study drug and remain on study may receive treatment consistent with local standard practice for their disease per Investigator judgement, as applicable.

Patients who discontinue study drug early for any reason during the Treatment Period (defined as the time the first dose of study drug is administered on Study Day 1 through completion of the Month 18 assessments) should complete the Early Drug Discontinuation visit and will be encouraged to remain on the study to complete the modified Month 9 and Month 18 efficacy assessments visits, prioritizing the primary and secondary assessments, where possible so that their experience is captured in the final analyses. If a patient discontinues study drug and completes the Early Drug Discontinuation visit within 3 months of Month 9 or Month 18 and remains on the study, they will not be required to complete the modified efficacy assessments at Month 9 and/or Month 18, as applicable depending on the time they discontinue study drug (Table 3).

Patients who discontinue study drug during the Legacy Treatment Extension Period or the RTE Period will be asked to return to complete the Early Drug Discontinuation visit (Table 3).

Patients who discontinue study drug, but who remain on study, may receive treatment consistent with local standard practice for their disease per Investigator judgment, as applicable. For patients who discontinue study drug and remain in the study, all AEs will be collected for 90 days after the last dose, thereafter, SAEs and AEs of clinical interest (see definition in Section 6.5.7.1) will be collected for the remainder of their participation in the study.

All patients who discontinue study drug will also be asked to complete safety follow-up visits, per the Follow-up Period schedule (see Table 4) until serum TTR levels return to $\geq 80\%$ of baseline (for up to 1 year after the last dose of study drug), or until the patient starts a TTR lowering regimen as a part of clinical care, whichever comes first; all patients will be followed

for a minimum of 3 months. Female patients of child-bearing potential who discontinue ALN-TTRSC02 will be followed until serum TTR levels return to $\geq 80\%$ of baseline.

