Abbreviations: ADA=antidrug antibodies; AE=adverse event; Con. Med.=concomitant medications; C-SSRS= Columbia-Suicide Severity Rating Scale; ECG=electrocardiogram; EOT=End of Treatment; EQ-5D-5L=EuroQuality of Life 5-Dimensions 5-Levels; EQ-VAS= EuroQuality of Life-Visual Analog Scale; FAP=Familial Amyloidotic Polyneuropathy; FU=Follow-up; HRdb=heart rate variability with deep breathing; KPS= Karnofsky Performance Status; LFT=liver function test; mBMI=modified body mass

index; 10-MWT=10-meter walk test; mNIS+7=modified NIS+7; NIS=Neurologic Impairment Score; NYHA=New York Heart Association; PE=physical exam; PK=pharmacokinetics; PND=Polyneuropathy Disability; QoL-DN=Quality of Life-Diabetic Neuropathy; R-ODS=Rasch-built Overall Disability Scale; TTR=transthyretin

Table 3 Notes:

- Dosing may be allowed outside of the study center (eg, the patient’s home) under certain circumstances as specified in Section 5.2.2.1 and Section 5.2.2.2. In addition, routine assessments and collection of relevant safety information may be collected outside the study center as specified in the beginning of Section 6.
- For the NIS; mNIS+7; HRdb;10-MWT performed as part of the Early Drug Discontinuation Visit and the Modified Month 9 and 18 Efficacy Visit(s): Two independent assessments will be performed on separate days (1 assessment on each day); the 2 assessments should be performed approximately 24 hours apart from each other but not more than 7 days apart.
- See Section 4.3 for instructions on early discontinuation of study drug procedures.
- SAE, AECI will be collected throughout the Follow-up Period; AEs will be collected until 3 months after the last dose of study drug.
- Dosing decisions may be made based on LFT results (Table 8) collected at the previous dosing visit (up to 14 weeks prior to dosing); in all cases, the most recently available LFTs should be used. LFT monitoring details are provided in Section 5.2.3.
For the patisiran cohort, LFTs should be performed according to patisiran visit windows and do not need to be available prior to dosing.

* The Early Discontinuation Visit applies to all periods of the study. [REDACTED]

^a Previously referred to as the 18-month Treatment Extension Period (per Amendment 3 and earlier); [REDACTED]

[REDACTED]	[REDACTED]	[REDACTED]	[REDACTED]	[REDACTED]	[REDACTED]	[REDACTED]	[REDACTED]	[REDACTED]	[REDACTED]	[REDACTED]	[REDACTED]

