1.7. Benefit-Risk Assessment

Based on available nonclinical and clinical data, with evidence of TTR reduction in the healthy subject study, TTR reduction by ALN-TTRSC02 is anticipated to beneficially impact disease progression in patients with hATTR amyloidosis, as has been shown with other available TTR lowering agents including patisiran and inotersen. The q3M and q6M SC regimens are infrequent, easy to administer, do not require premedication, and thus may maximize convenience and minimize overall burden of care. In the Phase 1 clinical study in healthy subjects, single SC doses up to the highest tested dose (300 mg) of ALN-TTRSC02 were well tolerated.

Patients with hATTR amyloidosis often suffer substantial loss in ambulation and mobility associated with other comorbidities that significantly impact activities of daily living and can make healthcare visits challenging. [REDACTED] aims to further minimize the need for frequent healthcare visits and further mitigate patient burden. This is consistent with global trends toward decreased healthcare encounters, the importance of which has been further highlighted by the COVID-19 pandemic.

Given the biological target of ALN-TTRSC02, the available nonclinical and clinical data, and the mode of administration, important potential risks for ALN-TTRSC02 are injection site reactions (ISRs), liver function test (LFT) abnormalities, and consequences of vitamin A deficiency. During the study, patients will be closely monitored, including evaluation of injection sites. As ALN-TTRSC02 is targeted for delivery to the liver, there is a potential for development of LFT abnormalities. Patients presenting with any laboratory result considered unacceptable as per exclusion criteria (see Section 4) at time of enrollment will be excluded from participation in this study, and LFTs will be routinely monitored throughout the study per the Schedule of Assessments. Criteria for dose withholding, modification and stopping ALN-TTRSC02 dosing due to LFT abnormalities are provided in Section 5.2.3. Detailed information about the known and expected benefits and risks of ALN-TTRSC02 and additional safety information may be found in the current edition of the ALN-TTRSC02 Investigator's Brochure.

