6.5.7. Adverse Events

6.5.7.1. Definitions

Adverse Event

According to the International Council for Harmonisation (ICH) E2A guideline Definitions and Standards for Expedited Reporting, and 21 CFR 312.32, IND Safety Reporting, an adverse event (AE) is any untoward medical occurrence in a patient or clinical investigational subject administered a medicinal product and which does not necessarily have a causal relationship with this treatment.

Serious Adverse Event

A serious adverse event (SAE) is any untoward medical occurrence that at any dose:

- Results in death
- Is life-threatening (an event which places the patient at immediate risk of death from the event as it occurred. It does not include an event that had it occurred in a more severe form might have caused death)
- Requires in-patient hospitalization or prolongation of existing hospitalization
- Results in persistent or significant disability or incapacity
- Is a congenital anomaly or birth defect
- Is an important medical event that may not be immediately life-threatening or result in death or hospitalization but may jeopardize the patient and may require intervention to prevent one of the other outcomes listed in the definition above (eg, events include allergic bronchospasm requiring intensive treatment in an emergency room or at home, blood dyscrasias, convulsions, or the development of drug dependency or abuse)

Adverse Events of Clinical Interest

The following are considered to be AEs of clinical interest:

- Alanine aminotransferase (ALT) or aspartate aminotransferase (AST) $>3\times$ upper limit of normal (ULN)
- Severe or serious injection site reactions (ISRs), ISRs that are associated with a recall phenomenon (reaction at the site of a prior injection with subsequent injections), recurrent ISRs that are increasing in severity, or ISRs that lead to temporary dose interruption or permanent discontinuation of ALN-TTRSC02
- An ISR is defined as a local reaction at or near the site of injection. “At or near” the injection site includes reactions at the injection site, adjacent to the injection site, or a reaction which may shift slightly away from the injection site due to gravity (eg, as may occur with swelling or hematoma). A systemic reaction which includes the injection site (eg, generalized urticaria, other distinct entities or conditions like lymphadenopathy that may be near the injection site) is not considered an ISR

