6.5.7.2. Eliciting and Recording Adverse Events

Eliciting Adverse Events

The patient and legal guardian, if applicable, should be asked about medically relevant changes in his/her health since the last visit. The patient should also be asked if he/she has been hospitalized, had any accidents, used any new medications, or changed concomitant medication routines (both prescription and OTC). In addition to patient observations, AEs will be documented from any clinically relevant laboratory findings, physical examination findings, ECG changes, or other findings that are relevant to patient safety.

Recording Adverse Events

The Investigator is responsible for recording non-serious AEs that are observed or reported by the patient after administration of the first dose of study drug regardless of their relationship to study drug through the end of study. Non-serious AEs will be followed until the end of study.

Events occurring after signing of the ICF and before study drug administration will be captured as medical history (see Section 6.1.3), while AEs that occur after study drug administration, and baseline events that worsen after study drug administration, must be recorded as AEs.

The Investigator is responsible for recording SAEs that are observed or reported by the patient after the time when the informed consent is signed regardless of their relationship to study drug through the end of study. SAEs will be followed until satisfactory resolution, until baseline level is reached, or until the SAE is considered by the Investigator to be chronic or the patient is stable, as appropriate.

For patients who discontinue study drug early and remain in the study, all AEs will be collected for 90 days after the last dose, thereafter, SAEs and AEs of clinical interest (see definition in Section 6.5.7.1) will be collected for the remainder of their participation in the study.

All AEs must be recorded in the source records for the clinical study center and in the eCRF for the patient, whether or not they are considered to be drug-related. Each AE must be described in detail: onset time and date, description of event, severity, relationship to study drug, action taken, and outcome (including time and date of resolution, if applicable).

For SAEs, record the event(s) in the eCRF and, as applicable, the SAE form.

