For AEs that are considered AEs of clinical interest (Section 6.5.7.1), the Sponsor or its designee should complete the supplemental AEs of Clinical Interest eCRF. Additional clinical and laboratory information may be collected. Refer to CRF completion guidelines for details on reporting events in the supplemental AEs of Clinical Interest eCRF.

For all ISRs, the Investigator, or delegate, should submit an Injection Site Reaction Signs or Symptoms eCRF, recording additional information regarding each injection site reaction that is entered on the AE eCRF (eg, symptom(s), injection site location, follow-up actions taken, etc.).

If patients develop ocular symptoms suggestive of vitamin A deficiency, for example reduced night vision or night blindness, the Investigator should consult with the Medical Monitor to determine if an ophthalmological assessment is needed. Any information collected during an ophthalmological assessment should be recorded in the eCRF and reports or images of ophthalmological assessments should be collected as well.

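### Vitamin A deficiency is the only named important potential risk without an AE-of-clinical-interest category, so after 90 days its non-serious eye events are captured at most through a conditional paragraph while TTR may still be suppressed

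*Protocol*

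**What the plan says.** All references are to the current protocol (Amendment 4) unless stated.

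- **Risks.** Section 1.7 states that "important potential risks for ALN-TTRSC02 are injection site reactions (ISRs), liver function test (LFT) abnormalities, and consequences of vitamin A deficiency".
- **AEs of clinical interest (AECIs).** Section 6.5.7.1 opens its list with "The following are considered to be AEs of clinical interest". It then gives ALT or AST above three times the upper limit of normal, and a restricted set of injection site reactions that begins "Severe or serious injection site reactions (ISRs), ISRs that are associated with a recall phenomenon". Nothing concerns vitamin A or the eye.
- **Collection after the last dose.** Section 4.3.1 sets the rule for patients who discontinue drug and remain in the study: "all AEs will be collected for 90 days after the last dose, thereafter, SAEs and AEs of clinical interest". Section 6.5.7.2 repeats it: "For patients who discontinue study drug early and remain in the study, all AEs will be collected for 90 days after the last dose". The notes to Table 3 say, without restricting the rule to early discontinuers: "SAE, AECI will be collected throughout the Follow-up Period; AEs will be collected until 3 months after the last dose of study drug".
- **General rule.** Section 6.5.7.2 makes the investigator responsible for recording non-serious AEs from the first dose to the end of study, and adds: "Non-serious AEs will be followed until the end of study".
- **Eye symptoms.** The same section says: "If patients develop ocular symptoms suggestive of vitamin A deficiency, for example reduced night vision or night blindness", the investigator consults the Medical Monitor on whether an eye assessment is needed. What such an assessment yields goes into the eCRF, with reports or images. No time limit is given.
- **Follow-up.** Sections 3.3 and 4.3.1 continue follow-up until TTR is back to at least 80% of baseline, for up to one year, or until another TTR-lowering regimen starts, with a minimum of 3 months.

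**The concern.** TTR carries retinol, so the vitamin A risk depends on how long TTR stays low rather than on the act of dosing. The protocol recognises that suppression outlasts the last dose, because it ties the end of follow-up to TTR recovery. Yet routine AE collection stops at a fixed 90 days or 3 months, and the exception that carries selected events further leaves this risk out.

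Reduced night vision is the protocol's own example of a relevant symptom, and it would often be non-serious. What is at stake is the ordinary AE record of such events late in follow-up: onset, severity, relationship to study drug, action taken and outcome. Section 1.7 also says that serum vitamin A does not reflect the total amount in the body, so the laboratory values do not replace a record of symptoms.

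**Working it through.** The protocol gives no figure for this point, so there is nothing of its own to reproduce. The check compares the passages and does simple arithmetic on the time windows.

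**1. Risks against AECI entries**

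| Risk in Section 1.7 | Entry in Section 6.5.7.1 |
|---|---|
| Injection site reactions | Yes, selected kinds |
| Liver test abnormalities | Yes, ALT or AST above 3 times the upper limit |
| Consequences of vitamin A deficiency | None |

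**2. Length of the gap**

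Inputs: all-AE window of 90 days (Sections 4.3.1 and 6.5.7.2) or 3 months (Table 3 notes); follow-up of 3 to 12 months (Section 4.3.1).

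- Longest: 365 − 90 = 275 days, and 275/365 = 75%. In months, 12 − 3 = 9, and 9/12 = 75%.
- Shortest: 3 − 3 = 0 months.

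This takes one year as the limit for everyone. The sentence on women of child-bearing potential who discontinue repeats the 80% criterion without restating that limit. If it is read as uncapped, their gap could be longer.

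**3. State of TTR at the cut-off**

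- Section 1.4.2: after one 25 mg dose in healthy subjects (n=12), the mean maximum reduction was 83%, maintained for 90 days. Remaining TTR is about 100 − 83 = 17% of baseline, against the 80% recovery criterion.
- Section 1.6: the predicted median trough reduction at steady state is 86%, which leaves about 14% of baseline. Trough on the 12-week schedule is day 84, and 90 − 84 = 6 days before the cut-off.

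Both figures indicate that collection narrows while TTR is still well below the recovery criterion.

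**4. What is captured after the cut-off**

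- A serious eye event is still collected, as an SAE.
- For a non-serious event with an ophthalmological assessment, the assessment information enters the eCRF. Section 6.5.7.2 does not say that the AE itself is then recorded with its usual fields.
- For a non-serious event where no assessment is judged necessary, the visible text requires no record.

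**5. Consistency of the end date**

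- Early discontinuers: the general rule and the 90-day rule stand in the same section, the second naming these patients. That is a rule with an exception, and it agrees with Section 4.3.1.
- Other patients in follow-up: the Table 3 note ends non-serious AE collection at 3 months, while Section 6.5.7.2 has it continue to the end of study. Section 3.3.1 lists completion of the Follow-up Period, up to one year, as one end-of-study criterion. These patients therefore have two possible end dates.

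**The case against.** The strongest reply is that the protocol already singles out these symptoms. The eye paragraph has no 90-day limit, calls for Medical Monitor consultation and collects assessment results. This stands against the stronger reading that a reader might infer, namely that eye symptoms simply leave collection after 90 days. It does not close the gap, because capture depends on an assessment being done and nothing says that the paragraph overrides the AE cut-off.

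Other points on that side:

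- **Redaction.** Section 4.3.1 refers to Table 4 for the follow-up schedule, and Table 4 is blacked out. The original protocol's Follow-up column included vitamin A samples and a physical examination, and Section 6.5.3 sends significant examination findings to the medical history or AE form. Table 4 may retain or extend this. That limits the finding, but the visible definition and cut-off still need to agree.
- **The contradiction.** A reader might infer that Section 6.5.7.2 contradicts Section 4.3.1. It does not. Moreover, the sentence about following non-serious AEs concerns events already recorded. Only the Table 3 note conflicts with the recording rule, and only for patients who did not stop early. One end-of-study criterion in Section 3.3.1 is redacted, so the extent of that conflict cannot be fully settled.
- **The other two risks.** They are not collected in full either. Milder liver test rises and ordinary injection site reactions fall under the same cut-off. The contrast is between partial AECI coverage and none.
- **Importance.** All AEs are collected during treatment, which may last up to 54 months. Section 1.7 says that the lowering of vitamin A does not result in severe deficiency, and all patients are told to take the recommended daily allowance. Nothing requires every important potential risk to be an AECI. These points keep the matter modest. They also suggest that any events would tend to be non-serious, which is the class affected.

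**Conclusion.** The point holds as a gap in safety data collection. Vitamin A deficiency is the only named important potential risk with no AECI category. After 90 days or 3 months from the last dose, its non-serious eye events are captured at most through a paragraph that depends on an assessment being done. The gap is at most about 9 of 12 months under a one-year limit, and zero for a patient followed only 3 months. The 75% figure is therefore a ceiling, and the protocol gives no basis for an average.

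A second, separate defect is the conflict between the Table 3 note and Section 6.5.7.2 on the end date for non-serious AEs in follow-up patients who did not stop early. Sites following one or the other would collect different data.

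A reader might infer that the trial cannot describe this risk at all. The documents do not support that: events during treatment, serious events, and late events that lead to an eye assessment all leave a record. No efficacy analysis is affected. The conclusion assumes that the redacted Table 4 adds no symptom collection of its own, and that the healthy-subject and modelled TTR figures are a fair guide to patients at the cut-off.

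**What to change.** 1. Add ocular AEs suggestive of vitamin A deficiency to the list in Section 6.5.7.1, using the examples already in Section 6.5.7.2. The existing AECI rule then carries them to the end of follow-up. Alternatively, state in Section 6.5.7.2 that these events are recorded as AEs throughout the Follow-up Period.
2. Reconcile Sections 4.3.1 and 6.5.7.2 (including its eye paragraph) and the Table 3 note, with Table 4, on one end date for non-serious AEs. Say plainly whether it differs between early discontinuers and other patients.

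The cost is one list item or sentence, one reconciled rule and a small eCRF update. Quarterly follow-up visits already exist, so no visit or procedure is added. The first option brings a few extra AECI forms and, under Section 6.5.7.3, notification of the sponsor within 24 hours for each event. The second option avoids both. Neither changes dosing or clinical management.
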